10.1.1 Demographic Data

Include date of birth (DOB), age, gender, race, and ethnicity.

10.1.2 Medical and Cancer History

A complete medical history will be obtained from each patient including the specifics of their advanced malignancy and molecular alterations. For female patients of child-bearing potential, the date of the last menstrual period will be noted. Smoking history and prior cancer therapy will be recorded. Data will be reviewed and updated at each visit.

10.1.3 Prior and Concomitant Medications

See [Section 8.5](#).

10.1.4 Vital Signs and Physical Examination

Height should be recorded at screening only. Body weight should be recorded at each visit.

Vital sign records should include body temperature, systolic/diastolic blood pressure (BP), and pulse rate. BP should be assessed on the same arm during the study.

Full physical examination evaluations at screening should include general appearance, skin, neck, eyes, ears, nose, throat, lungs, heart, abdomen, back, lymph nodes, extremities, and neurological examinations. Subsequent targeted physical exams should include body systems as appropriate.

Performance status (ECOG) should be assessed within 72 hours before start of study treatment and at each study visit (see Appendix 3).

10.1.5 Ophthalmology Examination

A full ophthalmic examination will be performed at the time points described in the SoA or when clinically indicated. They will include best-corrected visual acuity (BCVA), visual field examination (VF), intraocular pressure, external eye examination, and dilated fundoscopy. For additional details refer to study manual.

Any patient experiencing vision changes must stop taking ulixertinib and have an ophthalmic evaluation. Ulixertinib may be re-started when symptoms resolve.

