In order to monitor for potential hematologic toxicity in humans, routine clinical laboratory hematology tests, should be performed and any indication of abnormalities may result in further investigations.

Phototoxicity

Ulixertinib exhibits an absorbance peak in the range of UV-A/UV-B light, specifically at ~320 nm. In clinical studies with ulixertinib to date, 5 TEAEs of photosensitivity reaction in patients on 75mg (1 patient) and 600mg b.i.d. (4 patients) have been reported (all in study BVD-523-01).

Beyond dermatological monitoring (above), potential risks of direct phototoxic reactions induced by ulixertinib should be further minimized by advising patients to minimize sun exposure, use broad-spectrum sunscreens, and wear sunglasses. Patients will be informed that relevant sun exposure may occur even through glass, such as while driving.

Ophthalmological Effects

While the preclinical toxicology studies of ulixertinib have not revealed any exposure-dependent ophthalmological toxicities, based on clinical studies of MEK1/2 inhibitors which highlighted ocular toxicities that may reflect mechanistically attributable risks observable in a proportion of patients, clinical studies of ulixertinib have included close monitoring for ocular toxicities. In the clinical trials to date, the following ocular events have been rarely reported (n=115): visual impairment (7%), vision blurred (4%), photophobia (2%), retinal vein occlusion (<1%, reversible grade 3), vitreous floaters (<1%), chorioretinopathy (<1%), halo vision (<1%), and retinal detachment (<1%). Although it is not definitively understood whether ocular toxicities reflect primary pharmacology associated with global inhibition of the MAPK pathway, specific

management and exclusion criteria will be defined in this study protocol as the toxicities could potentially severely and irreversibly impact patient well-being.

Cardiac Effects

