7.2 EXCLUSION CRITERIA

Patients who fulfill one or more of the following criteria will not be eligible for inclusion in this trial:

1. Gastrointestinal (GI) condition that could impair absorption of study medication (specific cases e.g., remote history of GI surgery, may be enrolled after discussion with the medical monitor) or inability to ingest study medication.
2. Uncontrolled or severe intercurrent medical condition.
3. Known uncontrolled brain metastases. Stable brain metastases either treated or being treated with a stable dose of steroids/anticonvulsants, with no dose change in the previous 4 weeks, can be allowed.
4. Having received any cancer-directed therapy (chemotherapy, hormonal therapy, biologic or immunotherapy, etc.) within 28 days or 5 half-lives (whichever is shorter) prior to the first dose of study drug. Patients previously treated with radiotherapy must have recovered from the acute toxicities associated with such treatment.
5. Major surgery within 4 weeks prior to first dose.
6. Any use of an investigational drug within 28 days or 5 half-lives (whichever is shorter) prior to the first dose of study drug. A minimum of 10 days between termination of the investigational drug and administration of study drug is required. In addition, any drug-related toxicity except alopecia should have recovered to Grade 1 or less.
7. Prior therapy with any ERK inhibitor (e.g. LY3214996, LTT462).
8. Groups 1-4: Prior therapy with any BRAF and/or MEK inhibitor (e.g. encorafenib, dabrafenib, vemurafenib, binimatinib, trametinib, cobimetinib) is excluded. Prior BRAF and/or MEK inhibitor therapy is permitted for Groups 5 and 6.
9. For Part B, agents targeting BRAF or MEK kinases and experimental agents are not permitted as physician choice.
10. Pregnant or breast-feeding women.

11. Any evidence of serious active infections. Patients are allowed to enroll if they have been fever-free for at least 48 hours and are on an active treatment that is not prohibited in Appendix 1.
12. Any important medical illness or abnormal laboratory finding that would increase the risk of participating in this study (based on the investigator's judgment).
13. A history or current evidence/risk of retinal vein occlusion (RVO) or central serous retinopathy (CSR).
14. Concurrent therapy with any other investigational agent.
15. Concurrent therapy with drugs known to be strong inhibitors or inducers of CYP1A2, CYP2D6, and CYP3A4.

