8.1.3 Dose Interruptions and Adjustments

Patients experiencing unacceptable toxicity will have their treatment interrupted until the toxicity returns to \leq Grade 1 or pre-treatment baseline (whichever is more severe). Resumption of ulixertinib may occur at a lower dose level, aligning with capsule dose availability. Such dose adjustments will be done in consultation with the investigators and medical monitor of the study.

If a non-treatment related AE or toxicity-related dose delay lasts for > 21 days, treatment will be discontinued permanently, and the patient should be removed from study treatment.

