9 STUDY DRUG DISCONTINUATION AND PATIENT DISCONTINUATION/WITHDRAWAL

9.1 DISCONTINUATION OF STUDY DRUG

Discontinuation from the study drug does not mean discontinuation from the study, and remaining study procedures should be completed as indicated by the study protocol. If a clinically significant finding is identified (including, but not limited to changes from baseline) after enrollment, the investigator or qualified designee will determine if any change in patient management is needed. Any new clinically relevant finding will be reported as an AE.

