10.1.6 Laboratory Assessments

The following clinical laboratory tests will be performed:

- **Hematology** (blood sample: EDTA) – hemoglobin, hematocrit, white blood cells (WBC) count with differential, red blood cells (RBC) count, and platelet count.
- **Blood Chemistry** (blood sample: serum) – albumin, alkaline phosphatase (ALP), total bilirubin, calcium, chloride, creatinine, glucose, inorganic phosphorus, potassium, total protein, alanine aminotransferase (ALT), aspartate aminotransferase (AST), sodium, blood urea nitrogen (BUN), uric acid, lactic dehydrogenase (LDH), cholesterol, and triglycerides.
- If the total bilirubin concentration is increased above 1.5 times the upper normal limit, total bilirubin should be differentiated into the direct and indirect reacting bilirubin.
- **Urinalysis** – specific gravity, pH; semi-quantitative "dipstick" evaluation of glucose, protein, bilirubin, ketones, leukocytes, and blood and a microscopic examination including RBC, WBC, and casts will be performed if the dipstick is abnormal.
- **Pregnancy** – Beta-hCG Qualitative Urine or Serum

After Cycle 2, clinical chemistry (to include calcium and inorganic phosphorus), hematology, and urinalysis may be performed once per cycle or more frequently at the investigator's discretion.

Blood chemistry will be analyzed at each trial center by a certified laboratory and a report of the laboratory values will be sent to the investigator. The investigator or designee will review the laboratory report after receipt of the results and assess the clinical significance of all abnormal values. Results must be reviewed prior to dosing and appropriate action taken for any clinically significant abnormal values. Values will be documented on the laboratory report until stabilized, or the laboratory value returns to a clinically acceptable range (regardless of relationship to study medication) or baseline.

Any laboratory value that remains abnormal at the end-of-study (EOS) and that is considered clinically significant will be followed according to accepted medical standards for up to 30 days or until resolution of the abnormality or return to baseline.

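### Section 10.1.5 requires an ophthalmic evaluation after any vision change but permits restart when symptoms resolve, without requiring that the evaluation be completed, reviewed or free of an active lesion

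*Protocol*

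**What the plan says.** Protocol Section 10.1.5 gives the only eye-specific dosing rule: "Any patient experiencing vision changes must stop taking ulixertinib and have an ophthalmic evaluation. Ulixertinib may be re-started when symptoms resolve". The same section lists the components of the examination and points to a study manual for more detail.

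Section 4.2.1 explains why eye events get special treatment. It says that specific "management and exclusion criteria will be defined in this study protocol as the toxicities could potentially severely and irreversibly impact patient well-being". Among the eye events it reports are "visual impairment (7%), vision blurred (4%), photophobia (2%), retinal vein occlusion (<1%, reversible grade 3"), together with vitreous floaters, chorioretinopathy, halo vision and retinal detachment, each below 1%.

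Exclusion criterion 13 in Section 7.2 bars entry for "A history or current evidence/risk of retinal vein occlusion (RVO) or central serous retinopathy (CSR").

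The general interruption rule in Section 8.1.3 holds treatment for unacceptable toxicity until it falls to at most "Grade 1 or pre-treatment baseline (whichever is more severe"). It allows resumption at a lower dose and adds: "Such dose adjustments will be done in consultation with the investigators and medical monitor of the study". A dose delay longer than 21 days ends treatment. For a clinically significant finding, Section 9.1 says "the investigator or qualified designee will determine if any change in patient management is needed".

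**The concern.** The protocol orders a diagnostic examination and then leaves its result out of the decision it should inform. Read literally, a patient whose blurred vision has cleared may resume ulixertinib before the evaluation is done, before anyone has read it, or while it shows an active retinal lesion. Symptoms and lesions need not resolve together, and that is the usual reason for ordering an examination.

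The protocol sets its own standard here. Section 4.2.1 promises specific management because eye toxicity may be irreversible. The exclusion half of that promise names diagnoses. The management half delivers a mandatory stop and evaluation, but its restart condition refers to symptoms alone. What is at stake is the safety of a small number of patients. No estimate, test or sample size depends on it.

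**Working it through.** The plan gives no figure on this point to reproduce. The check has two parts: a comparison of the rules that could govern restart, and an estimate of how often they would apply.

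**1. Rules that could govern restart**

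| Section | When it applies | What it requires | Restart tied to eye result? | Medical monitor agreement? |
|---|---|---|---|---|
| 10.1.5 | Any vision change | Stop, evaluate; restart on symptom resolution | No | No |
| 8.1.3 | Unacceptable toxicity; any toxicity-related delay for the 21-day limit | Hold to Grade 1 or baseline; stop after more than 21 days | No | Consultation, for dose adjustments |
| 9.1 | Clinically significant finding | Investigator or designee decides; new relevant finding reported as an AE | No | No |
| 9.2, 9.3 | Unacceptable toxicity, change in condition, investigator's judgement, patient's best interest | Discontinue or withdraw | No | No |
| 10.4.4, 10.4.5 | All AEs | Follow-up to resolution or stabilization | No | No |
| 12.1.2 | Drug-related SAE or severe local reaction | Immediate Safety Monitoring Committee (SMC) review | No; review is not stated as a precondition for restart | No |
| 12.1.5.1 | Any AE or SAE | Periodic SMC review, at least twice a year | No | No |
| Schedule of Activities, ophthalmology footnote | Screening and when clinically indicated | Who examines and when | No | No |

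SAP Section 6.2 repeats the monitor consultation and also limits it to dose adjustments. In Section 8.1.3 the consultation follows the sentence on lower-dose resumption, so the plain reading does not reach a restart at the same dose. Consultation is also weaker than agreement.

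Section 10.1.6, on laboratory tests, offers a useful comparison: "Results must be reviewed prior to dosing and appropriate action taken for any clinically significant abnormal values". It is a review-before-dosing rule, not a restart rule after a toxicity hold. It does show that the protocol can place review of a result ahead of a dose, which 10.1.5 does not do.

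**2. How often the rule would apply**

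Inputs are the percentages in Section 4.2.1 with n=115. Only one count fits each rounded figure:
- 7%: 8/115 = 6.96%, so 8 (visual impairment)
- 4%: 5/115 = 4.35%, so 5 (blurred vision)
- 2%: 2/115 = 1.74%, so 2 (photophobia)
- below 1%: 1/115 = 0.87%, so 1 each for five terms (retinal vein occlusion, floaters, chorioretinopathy, halo vision, retinal detachment)

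Assume every listed term counts as a vision change. The document does not say how far the terms overlap within patients, so only bounds can be given:
- Full overlap: 8 patients, 8/115 = 7.0%
- No overlap: 8 + 5 + 2 + 1 + 1 + 1 + 1 + 1 = 20 patients, 20/115 = 17.4%

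Exact (Clopper-Pearson) 95% limits are the 0.025 quantile of Beta(x, n-x+1) and the 0.975 quantile of Beta(x+1, n-x):
- 8/115: 3.05% to 13.25%
- 20/115: 10.96% to 25.57%
- 1/115 (retinal vein occlusion): 0.02% to 4.75%

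For the three diagnoses in the fix below, the count runs from 1 (retinal vein occlusion and retinal detachment in one patient, chorioretinopathy not counted as central serous retinopathy) to 3 (three different patients, chorioretinopathy counted). That is 1/115 = 0.87% to 3/115 = 2.61%. Per planned group of 38 it is 38 x 1/115 = 0.33 to 38 x 3/115 = 0.99 expected patients.

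**The case against.** The strongest reply is that the general rules already protect the patient. Section 10.1.5 says the drug may be restarted; it does not direct it. An investigator holding an abnormal eye report can keep the drug stopped under 9.1, discontinue on judgement alone under 9.2, or withdraw the patient in the patient's interest under 9.3. The 21-day limit and AE follow-up do not need the event to be called unacceptable or serious, and the SMC reviews non-serious events periodically. This stands. It rules out the stronger reading a reader might infer, that the protocol forces re-dosing over a lesion or leaves it unregulated.

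A reader might also see a contradiction with exclusion criterion 13, since retinal vein occlusion and central serous retinopathy bar entry but do not expressly bar restart. The documents do not support that: the exclusion governs entry only.

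Two more points on the other side stand. The study manual is not available and could hold a restart rule, although the pointer to it follows the list of tests and Section 4.2.1 promised the criteria in the protocol itself. And the documents report no case of re-dosing with a persisting lesion; the one retinal vein occlusion is described as reversible.

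What the reply does not do is close the gap. Each of these rules gives authority to withhold drug or oversight of events. None makes restart wait for the eye result.

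**Conclusion.** The gap is real and narrow. After any vision change the protocol mandates an evaluation, yet it permits restart when symptoms resolve without requiring that the evaluation be completed, reviewed or clear of an active lesion. No rule clearly requires medical monitor agreement for a same-dose restart after a serious retinal event.

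Severity is a minor patient-safety improvement. The rule would be triggered in roughly 7% to 17% of treated patients, if every listed eye term counts as a vision change and the earlier experience carries over to this population. It would be wrong to read these figures, or the 0.87% for retinal vein occlusion, as ceilings or harm rates. They are sample estimates with wide intervals, and the share of patients with a lesion still present at restart is unknown. SAP Section 7.2 records early termination during Part A and gives no number treated, so no trial total can be stated. Confidence is limited by the unseen study manual.

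**What to change.** Replace the last sentence of Section 10.1.5 with:

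> Ulixertinib may be re-started only when symptoms have resolved and the ophthalmic evaluation has been completed and reviewed by the investigator and shows no ongoing clinically significant finding, subject to Section 8.1.3. If the evaluation shows RVO, CSR or retinal detachment, the medical monitor must agree before any restart, at any dose.

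Requiring review alone would not be enough, because a reviewed but persisting lesion could still be re-dosed.

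The evaluation is already mandatory; a repeat would be needed only to show that a finding has cleared. The costs are a short delay for review in about 7 to 17 per 100 treated patients, and one medical monitor contact in about 1 to 3 per 100, on the assumptions above. Some patients with a persisting finding would be held longer, and a few of them could pass the 21-day limit in 8.1.3 and lose treatment. Because the study ended early, the change matters mainly for any patient still on drug and for later ulixertinib protocols that reuse this text.

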10.1.6 Laboratory Assessments

The following clinical laboratory tests will be performed:

- **Hematology** (blood sample: EDTA) – hemoglobin, hematocrit, white blood cells (WBC) count with differential, red blood cells (RBC) count, and platelet count.
- **Blood Chemistry** (blood sample: serum) – albumin, alkaline phosphatase (ALP), total bilirubin, calcium, chloride, creatinine, glucose, inorganic phosphorus, potassium, total protein, alanine aminotransferase (ALT), aspartate aminotransferase (AST), sodium, blood urea nitrogen (BUN), uric acid, lactic dehydrogenase (LDH), cholesterol, and triglycerides.
- If the total bilirubin concentration is increased above 1.5 times the upper normal limit, total bilirubin should be differentiated into the direct and indirect reacting bilirubin.
- **Urinalysis** – specific gravity, pH; semi-quantitative "dipstick" evaluation of glucose, protein, bilirubin, ketones, leukocytes, and blood and a microscopic examination including RBC, WBC, and casts will be performed if the dipstick is abnormal.
- **Pregnancy** – Beta-hCG Qualitative Urine or Serum

After Cycle 2, clinical chemistry (to include calcium and inorganic phosphorus), hematology, and urinalysis may be performed once per cycle or more frequently at the investigator's discretion.

Blood chemistry will be analyzed at each trial center by a certified laboratory and a report of the laboratory values will be sent to the investigator. The investigator or designee will review the laboratory report after receipt of the results and assess the clinical significance of all abnormal values. Results must be reviewed prior to dosing and appropriate action taken for any clinically significant abnormal values. Values will be documented on the laboratory report until stabilized, or the laboratory value returns to a clinically acceptable range (regardless of relationship to study medication) or baseline.

Any laboratory value that remains abnormal at the end-of-study (EOS) and that is considered clinically significant will be followed according to accepted medical standards for up to 30 days or until resolution of the abnormality or return to baseline.

10.1.7 Electrocardiogram (ECG)

All patients require a single 12-lead ECG measurement. The parameters to be recorded are QT, QTc, QTC F, PR, and QRS. A standard 12-lead (with a 10-second rhythm strip) tracing will be used for all ECGs. Patients should be supine for 5 minutes prior to the ECG.

Patients with a normal ECG in screening do not need to have repeat ECGs in subsequent cycles unless clinically indicated.

10.1.8 Echocardiogram (ECHO) or Multi-Gated Acquisition (MUGA)

LVEF will be assessed by ECHO or MUGA performed at screening and as clinically indicated.

10.1.9 Disease Status

The decision for body areas to be scanned will depend on the extent of disease. Disease assessments must include all known or suspected disease sites. Imaging will be performed on the abdomen, chest, pelvis, and the site of the primary tumor if elsewhere.

Tumor measurements based on physical examination will occur at baseline and on the first day of each treatment cycle. Tumor assessments will be made by CT/MRI/Physical Exam prior to dose initiation, at the 1st protocol-specified tumor measurement evaluation at the beginning of Cycle 2 and then every 2 cycles, and at End of Treatment. Patients that discontinue study treatment for any reason other than disease progression, must continue to have disease assessments every 8 weeks (\pm 7 days) until disease progression or the initiation of subsequent anticancer therapy. The schedule of tumor assessments should be fixed according to the calendar, starting with cycle one day one, regardless of treatment delays or interruptions due to toxicity. The same imaging technique used to characterize each identified and reported lesion at baseline will be employed in the following tumor assessments.

10.1.10 Tissue Biopsy

Tumor biopsy during the screening period and during Visit 5 (Day 28) of treatment in Part A is required. If a patient has undergone a biopsy within \leq 6 months and has not received any anticancer treatment since undergoing the biopsy, archival tissue from this biopsy may be used to fulfill screening tissue requirements. Assays to investigate pharmacodynamic markers of ERK inhibition in addition to exploratory analysis to

evaluate adaptive response in pathways in addition to MAPK will be deployed. These may include, but are not limited to, RPPA, Nanostring, and RNA-exome. An optional tumor biopsy is requested at end of treatment; this is not a mandatory collection but strongly encouraged in patients relapsing following robust response to ulixertinib. Broad molecular profiling will be applied to end of treatment/at relapse tumor samples to aid scientific understanding of mechanisms of resistance to ERK inhibition.

10.1.11 Blood Samples for Pharmacokinetic (PK) Analysis

In Part A only, plasma samples will be collected for PK analysis at Visit 4, pre-dose. Patients need to be at steady state for this collection, which means 10 consecutive doses, or 5 consecutive days.

